5.6. Trial stopping criteria

The trial will be stopped if either of the following occurs:

- A serious adverse event that is considered to be at least possibly related to GSK3036656 in one or more subjects on active treatment
- Severe, clinically significant non-serious adverse events that are considered to be at least possibly related to GSK3036656 in 2 or more subjects on active treatment in the same group/cohort

If, following an internal safety review, it is appropriate to restart the trial, a substantial amendment will be submitted to the Medicines and Healthcare products Regulatory Agency (MHRA) and Independent Ethics Committee (IEC). The trial will not restart until the amendment has been approved by the MHRA and IEC.

5.7. Subject and Study Completion

A completed subject is one who has completed all phases of the study including the follow-up visit.

The end of the study is defined as the last subject's last visit.

6. STUDY TREATMENT

6.1. Investigational Product

The term 'study treatment' is used throughout the protocol to describe products received by the subject as per the protocol design.

	Study Treatment	
Product name:	GSK3036656	Placebo
Formulation description:	GSK3036656 capsules containing 5 mg, 25 mg or 100 mg of GSK3036656 as free base equivalent	Matching capsule containing Avicel PH 102
Dosage form:	Capsule	Capsule
Unit dose strength(s)/Dosage level(s):	5 mg, 25 mg and 100 mg	N/A
Route of Administration	Oral	Oral
Dosing instructions:	See Study Reference Manual	See Study Reference Manual
Physical description:	Swedish Orange Size 0 capsule with no identifying markings containing a white to slightly coloured powder	Swedish Orange Size 0 capsule with no identifying markings containing a white to slightly coloured powder
Method for individualizing dosage:	Capsules packed in separate HDPE bottles	Capsules packed in separate HDPE bottles

6.2. Treatment Assignment

Eligible subjects will receive a unique subject number which will be assigned in chronological order. Once a subject number has been assigned to a subject, it cannot be reassigned to another subject.

A randomisation schedule will be generated by Clinical Statistics, prior to the start of the study, using validated internal software, which will assign subjects to GSK3036656 or placebo during a specific period. The pharmacist would be sent a copy of the randomisation schedule by the GSK randomisation co-ordinator, together with instructions as to which subjects to dose on Days 1 and 2 in the case of sentinel dosing. The pharmacist will assign randomisation numbers accordingly and communicate those back to the site to enter in the case report form (CRF).

6.3. Planned Dose Escalation and Adjustments

After the initial dose of GSK3036656, the decision to proceed to each subsequent dose level will be made by the Dose Escalation Committee (DEC) based on safety, tolerability and preliminary pharmacokinetic data from the prior lower dose level (Further details regarding dose escalation can be found in the 201040 Dose Escalation Charter). In Part A, safety data for at least 5 days post-dose and PK data for at least 2 days (48 hours) postdose from at least 4 subjects who received active treatment at the prior lower dose level will be reviewed before dose escalation. In Part B, safety data for at least the first 1 week (7 days) of dosing and PK data for at least the first 2 days (48 hours) of dosing from at least 4 subjects who received active treatment at the prior lower dose level will be reviewed before dose escalation. The actual doses to be administered will be selected by the DEC and may involve either an increase or a decrease in the dose, or repeating the same dose.

The exposures (AUC, Cmax) expected with the next selected dose will be predicted by pharmacokinetic assessment and modelling, and by calculating Bayesian predictive probabilities as data permit (more details in Section 10.3.1).

In toxicology studies in dogs, heart valvular and vascular lesions have been observed at relatively high doses and exposures; no such lesions have been seen in rats at similar exposures. To avoid the risk of this adverse event in the FTIH subjects, exposures in the FTIH study will be limited to predefined levels. Based on discussions with the GSK Cardiovascular Safety panel, the study will aim to limit the maximum individual daily plasma AUC(0-24) and Cmax after single or repeat dose to 4.9 µg.h/mL and 0.443 µg/ml, respectively - a 30-fold margin from the corresponding dog NOAEL exposures of 147.0 µg.h/mL and 13.3 µg/ml at which no valvular or vascular lesions have been detected.

Note: The term “mean” applied to group human exposure parameters (e.g., AUC) in this section refers to Geometric Mean of a dose cohort.

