4. STUDY DESIGN

4.1. Part A (Single Dose)

Figure 1 Part A Schematic

★ Dose escalation meeting

- o One of the dosing periods will be a food effect group – the dose will be determined based on data from previous cohorts
- o There will be a 2 week washout between doses initially but the washout period may be modified depending on emerging data from previous cohorts.
- o Cohorts 1 and 2 will be dosed sequentially. If it is considered desirable to dose Cohorts 1 and 2 in an overlapping/interlocking fashion, approval will be sought from the Regulatory Agency first.

Up to two cohorts will be included in the single dose part (Part A). Each cohort will participate in up to 4 treatment (dosing) periods (including a food effect treatment period). Initially, there will be a 14 day wash out period for individual subjects between each dose level which is considered sufficient in light of the predicted half-life of GSK3036656 [on average, approximately 30 hours (range: 12 to 72 hours) based on the various preclinical extrapolation methods], however this may be revised once relevant PK data is obtained. Nine subjects per cohort will be enrolled and randomised to ensure adequate safety, tolerability and PK information is gained and a balanced randomisation is achieved across all treatment (dosing) periods.

During each treatment (dosing) period, GSK3036656 will be administered to 6 subjects and placebo will be administered to 3 subjects. As this is a FTIH study, each treatment (dosing) period will be staggered over 2 days. On Day 1 of each dose level, one subject will receive GSK3036656 and one subject will receive placebo. The remaining subjects within the dosing group will be dosed one day later provided satisfactory safety and tolerability is demonstrated for the subjects dosed on Day 1. A treatment (dosing) period does not have to be staggered if the dose administered is equal to or lower than a dose that has been already tested and found to be safe and well tolerated.

Subjects will attend the unit on Day -1 for assessments and a meal. The subjects will then fast overnight (at least 8 hours) and be dosed the following morning (Day 1). Dosing with food may also be done in Part A once results from the food effect analysis are available. Dividing the total dose for the treatment (dosing) period into 2 or 3 smaller doses administered within 24 hours may also be done. The decision to divide the total dose into

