7. STUDY ASSESSMENTS AND PROCEDURES

This section lists the procedures and parameters of each planned study assessment. The exact timing of each assessment is listed in the Time and Events Table Section [7.1](#)

The following points must be noted:

- If assessments are scheduled for the same nominal time, THEN the assessments should occur in the following order:
 1. 12-lead ECG and vital signs
 2. Blood draws.

Note: The timing of the assessments should allow the blood draw to occur at the exact nominal time.

- The timing and number of planned study assessments, including safety and PK assessments, may be altered during the course of the study based on newly available data (e.g., to obtain data closer to the time of peak plasma concentrations) to ensure appropriate monitoring.
- The change in timing or addition of time points for any planned study assessments must be documented in a Note to File which is approved by the relevant GSK study team member and then archived in the study sponsor and site study files, but this will not constitute a protocol amendment.
- **Part B outpatient visits:** If subjects are discharged on Day 4, they will be required to return to the unit daily for dosing and assessments. Safety assessments will include daily vital signs, AE and concomitant medication review and laboratory assessments on days 6, 10 and 15.
- The IEC and MHRA will be informed of any safety issues that require a protocol amendment or amendment of the Informed Consent Form.
- No more than 500 mL of blood will be collected over the duration of the study, including any extra assessments that may be required.

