7.1. Time & Events Table

Table 1 Part A

Part A	Screening	Day					Follow-up
		-1	1	2	3	4	
Days	-28 to -2						
Informed consent	X						
Inclusion/exclusion criteria ¹	X		X				
Medical/surgical history	X						X
Admission			X				
Inpatient stay			←	→			
Dose of GSK3036656 ²				X			
Echocardiogram ³	X						X
Discharge						X	X
Outpatient visit ⁴	X	X					X
Safety assessments							
Physical examination ⁵	X		X		X		X X
Height & weight ⁵	X						
Vital signs ⁶	X		X	X	X	X	X X
12-lead ECG ⁷	X			X	X	X	X X
Holter monitoring ⁸	←	→					
Telemetry ⁹			←	→			
Clinical laboratory assessments							
Screening tests (incl blood FSH & estradiol for female subjects only)	X						
Haematology, biochemistry and urinalysis ¹⁰	X		X		X		X X
Pregnancy test (female only) ¹¹	X		X				
Urine drug screen, alcohol & smoking breath tests	X		X				
PK samples							
Blood for PK GSK3036656 ¹²				X	X	X	X
Total urine collection ¹³				X	X	X	X
Concomitant therapy review ¹⁴	←						→
Adverse events ¹⁴	←						→

1. Inclusion/exclusion criteria will only be assessed at Day-1 of the first period.
2. In the event of a divided dose, alterations to event timepoints may be communicated in a filenote. For the food effect assessment, the selected dose will be given with a high fat meal.
3. Echocardiograms may be done at a separate screening visit.
4. When there is Holter monitoring at screening, subjects will return after 24 h to have the Holter removed.
5. Brief physical examination will be done at admission (Day-1) and in the morning on Days 2 and 4 in each treatment session. Full physical examination will be done at screening and follow-up (to include height and weight at screening only).
6. Blood pressure, heart rate, tympanic temperature and respiratory rate. Vital signs will be recorded: at pre-dose and at 0.5, 1, 2, 3, 4, 6, 12, 24, 48 and 72 h after dosing on Day 1.

7. ECGs will be recorded at pre-dose and at 0.5, 1, 2, 3, 4, 6, 12, 24, 48 and 72 h after dosing on Day 1. Triplicate measurements (about 2-5 mins apart) will be taken at pre-dose; single measurements will be taken at all other time points.
8. 24 h Holter monitoring at screening only.
9. Telemetry will be recorded from -1 h pre-dose until 24 h post-dose
10. Haematology, clinical chemistry, and urinalysis will be done at Day-1 and at 24 and 72 h post-dose.
11. Pregnancy testing of female subjects only. At screening pregnancy test will be done using the blood sample; urine pregnancy test will be done on admission.

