12. Blood samples for assay of GSK3036656 will be taken: at pre-dose and at 0.25, 0.5, 0.75, 1, 1.5, 2, 3, 4, 6, 8, 12, 15, 24, 36, 48 and 72 h after dosing on Day 1.
13. Total urine collections for GSK3036656 will be performed at the following time points: pre-dose and 0-6, 6-12, 12-24, 24-48 and 48-72 h after dosing on Day 1.
14. AEs and concomitant medications will be recorded collected from the start of informed consent until the follow-up contact.

Table 2 Part B

Part B	Screening	Day																	Follow-up
		-1	1	2	3	4	5	6	7	8	9	10	11	12	13	14	15	16	28
Days	-28 to -2																		
Informed consent	X																		
Inclusion/exclusion criteria	X		X																
Medical/surgical history	X																		X
Admission			X																
Inpatient stay				←														→	
Dose of GSK3036656 ¹				X	X	X	X	X	X	X	X	X	X	X	X	X			
Echocardiogram ²	X																		X
Discharge																	X		X
Outpatient visit ³	X	X																X	X
Safety assessments																			
Physical examination ⁴	X		X		X		X		X			X					X		X
Height & weight ⁴	X																		
Vital signs ⁵	X		X	X	X	X	X	X	X	X	X	X	X	X	X	X	X	X	
12-lead ECG ⁶	X			X	X	X	X		X			X				X			X
Holter monitoring ⁷		←	→																
Telemetry ⁸				←	→														
Clinical laboratory assessments																			
Screening tests (incl blood FSH & estradiol for female subjects only)	X																		
Haematology, biochemistry and urinalysis ⁹	X		X			X		X				X				X			X
Serum pregnancy test (female only) ¹⁰	X		X																
Urine drug screen, alcohol & smoking breath tests	X		X																
PK samples																			
Blood for PK GSK3036656 ¹¹				X	X	X	X								X	X	X	X	X
Total urine collection ¹²				X	X										X	X			
Concomitant therapy review ¹³		←																→	
Adverse events ¹³		←																→	

1. Dosing of GSK3036656 should be at approximately the same time each day. In the event of a divided dose, alterations to event timepoints may be communicated in a filenote.
2. Echocardiograms may be done at a separate screening visit.
3. When there is Holter monitoring at screening, subjects will return after 24 h to have the Holter removed.
4. Brief physical examination will be done on Days-1, 2, 4, 6, 10, and 15. Full physical examination will be done at screening and follow-up (to include height and weight at screening only).

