8.1.2. Method of Detecting AEs and SAEs

Care will be taken not to introduce bias when detecting AEs and/or SAEs. Open-ended and non-leading verbal questioning of the subject is the preferred method to inquire about AE occurrence. Appropriate questions include:

- “How are you feeling?”
- “Have you had any (other) medical problems since your last visit/contact?”

- “Have you taken any new medicines, other than those provided in this study, since your last visit/contact?”

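### Part A escalation requires 5 days of post-dose safety data, but Table 1 schedules no check or AE enquiry after 72 h until the next Day -1 or follow-up, so an early review would cover 72 to 120 h by spontaneous reports only

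*Protocol*

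**What the plan says.** Protocol Section 6.3 sets the escalation condition: "In Part A, safety data for at least 5 days post-dose", together with 48 h of PK data, from at least 4 actively treated subjects, must be reviewed before the dose goes up. It refers to a Dose Escalation Charter for further detail; the Charter is not among the documents.

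In Table 1 (Section 7.1; same schedule in SAP 10.2.1), vital signs, ECGs and PK samples run to 72 h, and "Haematology, clinical chemistry, and urinalysis will be done at Day-1 and at 24 and 72 h post-dose". Section 4.1 keeps subjects in the unit until the 72 h sample and then allows discharge at the investigator's discretion. The next scheduled events are Day -1 of the following period and the follow-up visit about 14 days after the last dose. On spacing, Section 4.1 says "Initially, there will be a 14 day wash out period for individual subjects between each dose level". The washout may be revised, but the same subjects must have at least 4 half-lives between doses.

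On AEs, footnote 14 of Table 1 says "AEs and concomitant medications will be recorded collected from the start of informed consent until the follow-up contact". Section 8.1.1 ties collection to the time points of that table. Section 8.1.2 relies on open questions at visits, such as one about "medical problems since your last visit/contact".

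For Part B, Section 6.3 asks for 7 days of safety data. Section 7 matches this for subjects discharged on Day 4, who return each day: "Safety assessments will include daily vital signs, AE and concomitant medication review".

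Section 4.1 lets Cohort 2 begin once Cohort 1 has finished dosing; Cohort 1 follow-up is not a condition.

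**The concern.** The escalation rule looks 5 days ahead and the schedule stops at 3. The 48 h PK requirement in the same sentence is fully covered by the sampling plan; the 5-day safety requirement is not. If the schedule is followed as written and the committee meets soon after Day 5, nobody will have asked the subjects anything about the last 2 of those 5 days.

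The stake is the safety of the next people dosed. Escalation steps may be up to 6-fold (Section 6.3.1), and the first escalation stopping criterion (Section 5.5) compares clinically significant AEs on active drug with those on placebo. An event that begins after discharge and is not volunteered would be missing from that comparison. Drug may also still be present during the window that is not actively covered.

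**Working it through.** **Timeline check against the plan's own figure.** Screening 28 days + three 14-day intervals between four doses + 14 days to follow-up = 28 + 42 + 14 = 84 days = 12 weeks. This reproduces the Part A duration of about 12 weeks in Section 4.2, so 14-day spacing is the planned case.

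**Size of the gap.**
- Required window (Section 6.3): 5 × 24 = 120 h.
- Last in-period check (Table 1): 72 h.
- No scheduled ascertainment: 120 − 72 = 48 h; 48/120 = 40%. This holds for any review that precedes the next scheduled visit.
- Next Day -1 at 14-day washout: (14 − 1) × 24 = 312 h.
- Follow-up: 14 × 24 = 336 h, which is 336 − 72 = 264 h after the last check and 336 − 120 = 216 h (9 days) after the 5-day mark.

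**Where Day -1 closes the gap.** Before a within-cohort step at 14 days, the same subjects return at about 312 h for laboratory tests, vital signs and a brief examination, and can be asked about the interval. That is before the higher dose.

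**Where it does not: Cohort 1 to Cohort 2.** New subjects are dosed, and Cohort 1's next scheduled enquiry is follow-up. The 5-day rule alone would allow Cohort 2 dosing up to 9 days before it. This needs Cohort 1's last period to be the dose escalated from. Section 6.3.1 allows that order: fed dosing may start once two fasted dose levels have known exposures, so a fed third period can be followed by a higher fasted fourth. If the fed period comes last, it repeats a dose already tolerated fasted (Section 4.1.1). Subjects given the top fasted dose have then already come back for Day -1, and the exposure does not arise.

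**Where it does not: shortened washout.** At the 4-half-life minimum, Day -1 falls at 4 × t½ − 24 h. This is before 120 h when t½ < 144/4 = 36 h. At 30 h it is 4 × 30 − 24 = 96 h. For half-lives under 30 h the 5-day rule is the binding limit for an escalation, so Day -1 still falls no earlier than about 120 − 24 = 96 h. The part left without a scheduled enquiry is then at most 24 h, and the subjects are back in the unit for it.

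**Drug remaining**, assuming single-exponential decline, 0.5^(time/t½), over the half-life range predicted in Section 4.1:

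| t½ | at 72 h | at 120 h |
|---|---|---|
| 12 h | 1.6% | 0.1% |
| 30 h | 18.9% | 6.3% |
| 72 h | 50% | 31.5% |

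**The case against.** The strongest reply is that the rule protects itself. A committee with nothing collected for 72 to 120 h arguably does not have 5 days of data and must wait or obtain it. AE recording does not stop at 72 h: the AE row of Table 1 is a continuous span to follow-up. Sections 7 and 8 allow time points to be added. The Charter may already specify a contact. This stands against one tempting inference, that the 5-day rule contradicts the schedule or cannot be met. The documents do not support that reading, because the rule can be met by waiting for the next visit. Nor do they show that any escalation would go ahead without data. What remains is that nothing in them ties the review to that visit or requires an enquiry before it.

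Second, a late event would often surface anyway. Section 5.6 stops the trial for one possibly related SAE, or for severe possibly related AEs in 2 active subjects of a cohort, and SAEs must be reported within 24 h. This also stands. It confines the residual risk mainly to unreported, mostly non-serious events. Sentinel dosing limits first-day exposure at the new level to one active subject, but it does not recover late events from the level before.

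Third, the exposure is conditional on period order, review timing and washout. That is correct, and it is why the point is minor.

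Fourth, Part B's daily attendance exists for dosing, so the contrast does not show a deliberate choice for Part A. It shows only that rule and schedule agree there.

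**Conclusion.** The mismatch holds as a minor one. As scheduled, the last 48 h of the 120 h that Section 6.3 relies on are not actively collected before the next Day -1 or follow-up. The gap matters at the Cohort 1 to Cohort 2 step if Cohort 1 ends on the dose being escalated from. It matters to a lesser degree within a cohort if the washout is cut so that Day -1 precedes 120 h.

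A reader might infer that the stopping rules are undermined or the results biased. The documents do not support this: no endpoint or estimate depends on the window, and the stopping criteria are unchanged. Only the completeness of the AE information behind an early review is in question.

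The conclusion assumes a review soon after Day 5, cohorts dosed sequentially as planned, and no contact already required by the Charter. The drug-remaining figures also rest on preclinical half-life predictions and a single-exponential decline.

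**What to change.** Add to Table 1 and SAP 10.2 a documented telephone enquiry about AEs and concomitant medication, at or after 120 h from each subject's own dose. The subject's own dose matters because dosing may be staggered over two days. Call all subjects in every Part A period that will support an escalation, and require the call to be complete for the 4 or more active subjects the committee counts. Calling everyone keeps the site blinded; the unblinded sponsor can confirm that enough of those reached were on active drug. If the Charter already requires such a contact, a cross-reference in Section 6.3 and Table 1 is enough.

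A call collects symptoms only. Laboratory, ECG and vital-sign data would still end at 72 h, so Section 6.3 should say that the 72 to 120 h data are AE data.

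The cost is up to 9 short calls per period, with no extra visit or sample. Delay should be negligible: the committee must wait 5 days anyway and needs 4 of 6 active subjects, so 2 could be unreached. Section 7 lets a time point be added by Note to File, "but this will not constitute a protocol amendment", but that is permission and does not make the contact happen.

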6.3.1. Dose escalation in Part A

In Part A, bigger dose escalation steps may be allowed at lower doses and systemic exposures as the expected risk of adverse events at these exposures is low. At higher doses, smaller dose escalation steps will be used to minimize the risk of adverse events and gastrointestinal intolerance.

The following rules will guide dose selection in Part A:

1. No dose escalation to the next dose will be higher than 6-fold.
2. Once the dose is ≥ 300 mg, any further dose escalation will be no higher than 3-fold irrespective of the observed exposures.
3. The highest dose in Part A will not exceed 1500 mg.
4. A proposed dose will be acceptable if the predicted probability of an individual exceeding a Day 1 plasma AUC (0-24) of 4.9 µg.h/mL or Cmax of 0.443 µg/mL, as estimated by PK modeling and Bayesian analysis (if feasible), is no more than 10%.

5. Based on prior PK data, individual doses may be adjusted, if needed, such that a predicted individual Day 1 AUC (0-24) or Cmax does not exceed 4.9 $\mu\text{g.h/mL}$ or 0.443 $\mu\text{g/mL}$, respectively.

Dosing with food in Part A will be initiated after the exposures achieved with at least two dose levels administered in a fasted state are already known.

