10.3.1. Interim Analysis

No formal interim analyses are planned for this study. However, safety, tolerability, and pharmacokinetic data will be reviewed before each dose escalation in Part A (single dose) and Part B (repeat dose), and prior to the investigation of the food effect.

The relationship between dose and plasma GSK3036656 exposure, and associated variability will be characterized by a power model once data are available from 3 dose levels. Prior to that, prediction of the human exposure at the next dose will be based on population PK modelling (if feasible) or on the assumption of dose–exposure proportionality (i.e., doubling the dose gives an approximate doubling of exposure). If prior PK results show less than proportional increase in exposure with increasing dose, the prediction will be based on the assumption that the fold exposure increase to fold dose increase ratio will be the same with the current dose escalation as it was with the previous one. If prior PK results show more than proportional increase in exposure with dose, subsequent dose escalations will not be higher than 3-fold. The power model will be updated as data become available throughout the study. During dose escalation, and once data is available from 3 doses, a Bayesian predictive probability that an individual will have $AUC(0-24)$ greater than 4.9 $\mu\text{g.h/mL}$ or a C_{max} greater than 0.443 $\mu\text{g/mL}$,

will be calculated for the next dose level and used together with safety and tolerability data to aid the next dose selection.

The Bayesian predictive probability will be based on Whitehead's model [[Whitehead, 2001](#)]:

$$\log(y_{ij}) = \theta_1 + \theta_2 \cdot \log(d_{ij}) + \varepsilon_{ij}$$

where

- y_{ij} is the observed or predicted log-AUC variable (AUC[0-24]) or log-Cmax of the j-th dose d_{ij} administered to the i-th subject
- θ_1, θ_2 are population intercept and slope, respectively.
- ε_{ij} is a random error term, with mean zero and variance σ^2 .

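### Rule 2 in protocol 6.3.1 caps steps only after 300 mg has been given, so doses of 155 to 295 mg permit a higher next dose than 300 mg does; a low-probability gap that one sentence closes

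*Protocol*

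**What the plan says.** Protocol 6.3.1 sets five rules for choosing doses in Part A. Its introduction says that "bigger dose escalation steps may be allowed at lower doses and systemic exposures" and then that "At higher doses, smaller dose escalation steps will be used to minimize the risk of adverse events and gastrointestinal intolerance".

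- Rule 1: "No dose escalation to the next dose will be higher than 6-fold".
- Rule 2: from 300 mg on, "any further dose escalation will be no higher than 3-fold irrespective of the observed exposures".
- Rule 3: an absolute ceiling of 1500 mg.
- Rule 4: the predicted probability that an individual exceeds a Day 1 AUC(0-24) of 4.9 µg.h/mL or a Cmax of 0.443 µg/mL must be no more than 10%.
- Rule 5: "individual doses may be adjusted, if needed, such that a predicted individual Day 1 AUC (0-24) or Cmax does not exceed" those limits.

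Two other sections bear on step size. Section 10.3.1 adds a conditional cap: "If prior PK results show more than proportional increase in exposure with dose, subsequent dose escalations will not be higher than 3-fold". Section 6.3 requires review before each escalation ("In Part A, safety data for at least 5 days post-dose and PK data for at least 2 days (48 hours) postdose"), based on at least 4 subjects given active drug. It also refers to a Dose Escalation Charter for further detail; the charter is not among the documents.

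**The concern.** Rule 2 is worded for escalations that come after a dose of 300 mg or more. A step that crosses 300 mg starts from a lower dose, so among the fold limits only rule 1 and the ceiling apply to it. The permitted next dose therefore falls when the current dose rises from 295 to 300 mg. The largest absolute jumps are allowed just below the threshold at which the section becomes cautious.

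Rule 2 is also the one step rule that holds whatever the observed exposures. It is meant for the case where plasma levels are low and the exposure limits do not restrain the next dose. Tolerability that does not follow plasma exposure is the remaining worry there, and the section itself names gastrointestinal intolerance. In that case the written fold limit is looser just below 300 mg than at 300 mg.

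**Working it through.** **Step sizes under rules 1 to 3.** The start is 5 mg (protocol 4.1). Capsules of 5, 25 and 100 mg (6.1) give a 5 mg grid. The largest next dose is min(6d, 1500) for d below 300 mg and min(3d, 1500) for d of 300 mg or more.

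| Current dose (mg) | Largest next dose (mg) | Fold |
|---|---|---|
| 150 | 900 | 6.0 |
| 180 | 1080 | 6.0 |
| 250 | 1500 | 6.0 |
| 295 | 1500 | 5.1 |
| 300 | 900 | 3.0 |

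The only fall on the grid is between 295 mg (1500) and 300 mg (900). Every current dose from 155 to 295 mg permits more than 900 mg. On the fastest path (5, 30, 180, 1080, 1500 mg) rule 2 limits no step, since 1080 to 1500 mg is only 1.4-fold.

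**Checks on the plan's own figures.** The exposure limits reproduce: 147.0/30 = 4.9 and 13.3/30 = 0.443. Section 4.5 gives a probability below 1% of exceeding the AUC limit at 5 mg. Take the lowest predicted clearance, 1.1 mL/min/kg, with F = 1 and 70 kg. Then CL = 1.1 × 0.06 × 70 = 4.62 L/h and the median AUC is 5/4.62 = 1.08 µg.h/mL. With a 50% CV, SD(log) = √ln 1.25 = 0.472, and P(AUC > 4.9) = 0.07%. This agrees with the protocol.

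**Where rule 4 stops escalation on the lowest predicted exposure.** From 4.5: CL 7.2 mL/min/kg, F 60%, V 3.5 to 4.5 L/kg, and 50% CV for CL. Assumed here: 70 kg (315 L / 4.5 L/kg), one compartment, bolus input, and the same 50% CV for Cmax.

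- The 90th percentile over the median is exp(1.2816 × 0.472) = 1.832. The median limits are 4.9/1.832 = 2.67 µg.h/mL and 0.443/1.832 = 0.242 µg/mL.
- CL = 7.2 × 0.06 × 70 = 30.24 L/h.
- AUC(0-24) per mg = F/CL × (1 − exp(−24 CL/V)). Cmax per mg = F/V.
- V 4.5 L/kg: 0.01786 and 0.001905 per mg, so the single-limit ceilings are 150 mg (AUC) and 127 mg (Cmax).
- V 3.5 L/kg: 0.01882 and 0.002449 per mg, so the ceilings are 142 mg and 99 mg.

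Rule 4 is one limit on exceeding AUC *or* Cmax, so the relevant ceiling is the dose at which P(AUC > 4.9 or Cmax > 0.443) = 10%. With a bivariate lognormal and correlations of 0, 0.5 and 0.9, it is 115, 118 and 124 to 125 mg for V 4.5 L/kg, and 95, 96 and 98 to 99 mg for V 3.5 L/kg.

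**How far below that prediction exposure must be.** If exposure is proportional to dose, the fold is dose divided by joint ceiling.

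| Dose that rule 4 must pass (mg) | V 4.5 L/kg | V 3.5 L/kg |
|---|---|---|
| 900 (rule 2 begins to bind) | 7.2 to 7.8 | 9.1 to 9.5 |
| 1080 | 8.7 to 9.4 | 11.0 to 11.4 |
| 1500 | 12.0 to 13.0 | 15.2 to 15.8 |

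**The case against.** The strongest reply is that the gap is remote and well surrounded by other controls. Most of that stands.

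- **Exposure.** For 1080 mg to pass on AUC with proportional PK, the median at 180 mg must be at most 2.67/6 = 0.45 µg.h/mL, about 11-fold below the limit. The section expressly allows bigger steps when exposures are low. A reader might infer that the rules contradict the section's aim. That goes too far: rules 1 to 3 are outer limits that guide the Dose Escalation Committee, and the same section tells it to use smaller steps at higher doses.
- **Other controls.** Rules 4 and 5, committee review of 5-day safety and 48-hour PK data, sentinel dosing and the stay to 72 hours all apply. The total dose may be divided into 2 or 3 parts within 24 hours (4.1). Section 5.5 stops escalation on an adverse-event excess over placebo whatever the PK, and on an exposure plateau; 5.6 stops the trial. On the fastest path, 180 to 1080 mg is the third escalation, so the Bayesian probability in 10.3.1 is available. Tolerability is therefore not left to rule 4 alone.
- **The charter.** It may already limit steps that cross 300 mg.

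What remains is narrow. None of the available text sets a fold limit for a crossing step when PK is low and dose-proportional. The 3-fold cap in 10.3.1 needs more-than-proportional PK. Rule 2 itself first binds at about 7- to 9.5-fold below prediction, so a sponsor who thought that range worth a rule has reason to close a gap that opens only slightly further out.

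**Conclusion.** The wording gap is real, small and cheap to close. Under rules 1 to 3, current doses of 155 to 295 mg permit a higher next dose than 300 mg does. It matters only if exposure is dose-proportional and about 9- to 11-fold (1080 mg) or 12- to 16-fold (1500 mg) below the lowest prediction. On that prediction rule 4 ends escalation at about 95 to 125 mg.

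The folds are approximate. They rest on 70 kg, one compartment, bolus input and a 50% CV for both measures. Slower absorption would lower the Cmax contribution and so the folds; a distribution phase could raise them. Dividing by the single-limit AUC or Cmax ceilings would make the gap look nearer than rule 4's joint limit allows.

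A reader might infer that volunteers could be taken past the exposure limits, or that the main exposure safeguard is defective. The documents do not support either reading: rule 4 applies to every proposed dose, including one reached by a crossing step. No analysis or sample size is affected. This is a point to consider, not a required change.

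**What to change.** Add to rule 2: *no escalation from a dose below 300 mg will exceed 900 mg.* On the 5 mg grid the permitted next dose then never falls as the current dose rises. 1500 mg is still reached in five dose levels (5, 30, 180, 900, 1500 mg), as now, within the up to 8 dosing periods of Part A.

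A stricter option also works: *any escalation to a dose of 300 mg or more will be no higher than 3-fold.* It too reaches 1500 mg in five levels (5, 30, 180, 540, 1500 mg). It also bars steps such as 75 to 300 mg, which cause no inversion, and holds doses of 50 to 95 mg to a next dose of at most 295 mg. The choice between the two is the sponsor's. The 900 mg limit is the narrower repair, though it still allows 150 to 900 mg (6-fold).

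The cost is one sentence in the protocol and smaller steps across 300 mg: from 180 mg the most would be 900 mg, or 540 mg under the stricter option, instead of 1080 mg. If the charter already covers crossing steps, a cross-reference in rule 2 would be enough.
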